Treatment Effect Evaluations:	Subject Comfort will be evaluated using the Visual Analog Scale assessing Comfort following rTMS stimulation. Depression will be evaluated by PHQ-9. Preference will be evaluated by asking the patient if they prefer the current treatment, last treatment, or if they cannot determine a difference.
Safety Evaluation:	Safety will be monitored by comparing the type, frequency, and severity of adverse events as occurring during the different treatment protocol administrations.
Statistical Analysis:	Endpoints will be analyzed for statistical and clinical significance.

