13 STUDY PROCEDURES

13.1 Study Visits

This is a prospective, randomized, single blind, cross-over study in an adult population. Only patients who have already consented to treatment with rTMS for MDD as diagnosed and prescribed by their treating physician will be enrolled in this study.

The study consists of up to 10 visits; Visit 1 for subject screening and Visits 2-10 for treatment administration which will be conducted concurrently with the subjects scheduled rTMS stimulation sessions. Study visits are estimated to take approximately 30 minutes in addition to the patient's regular rTMS treatment visits.

The study visits will be conducted in 2 phases:

Ramp Phase: The intent of the first 1-5 treatment visits is to evaluate the differences between treatment groups on subject comfort as the subjects are ramped to the prescribed treatment dose. This phase will also evaluate the impact of the two treatments on the ability and the time to achieve the prescribed treatment dose.

Crossover Phase: The intent of the crossover phase is to evaluate comfort differences and subject treatment preference between treatment groups and within subjects. In addition, the ability, and the time to reach the prescribed dose for those subjects who may not have reached it in the first 5 treatment sessions will continue to be assessed.

Details of the study visits are described below and on the subject flow diagram in section 14.2.

Screening/Baseline Study Visit

During Visit 1, the subject will be informed about the study and will be screened for eligibility to participate against the inclusion and exclusion criteria (including medication and medical

history). Eligible subjects will have the study and consent process explained to them and be provided the informed consent form to sign, or to return signed on Day 1 of TMS Treatment.

Ramp Phase:

Treatment Visit 1

Once signed consent is obtained, in addition to the treating clinicians' normal TMS instruction, subjects will receive instruction about the study procedures including the completion of comfort, preference and depression scales at the time of treatment for up to 9 treatments. Medication changes and recent medical history, including adverse events will be reviewed.

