### **6.3 Handling of Missing Data**

All attempts will be made to limit the amount of missing data. Unless otherwise specified, no attempt will be made to impute missing data. If a data point is missing, that data point will not contribute to that portion of the analysis. The number of evaluable observations will be reported in analysis so that extent of missing data can be assessed.

In the case of partial adverse event onset date or date of death, the unknown portion of the date of the event will be imputed. If the month and year are known, the 15th of the month will be used for analysis. In the rare case that the date is fully unknown, the date will be imputed as the Date of first day of the Dose Ramp Phase. Imputation of partial dates is subject to the condition that it must occur on or after the informed consent date. In the case where the imputed date is prior to the informed consent date,

Statistical Analysis Plan		Page 10 of 18
Sponsor Neuronetics	Study Comfort Start	Version 1.0

the date of informed consent will be used. As death cannot occur before any documented subject contact, for date of death the imputed date of death must occur on or after last known contact in study.

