## **6.6 Analysis of Study Endpoints**

### **6.6.1 Primary Safety Endpoint**

Comparison of the incidence, severity, and frequency of Adverse Events (AE) & Adjustments in Treatment Location between the experimental and the control group will be made descriptively.

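### SAP 6.3 imputes a day-missing adverse-event onset to the 15th of the month with no upper bound, which is too coarse for a study of about two weeks and usually misplaces the event relative to treatment

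*SAP*

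**What the plan says.** SAP 6.3 (Handling of Missing Data) imputes the unknown part of an adverse-event onset date or a date of death.

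- Day missing: "If the month and year are known, the 15 th of the month will be used for analysis".
- Date fully missing, which the SAP calls rare: "the date will be imputed as the Date of first day of the Dose Ramp Phase".
- Bound: "it must occur on or after the informed consent date"; an imputed date earlier than consent is replaced by the consent date. Imputed deaths are also bounded by last known contact. Imputed onsets have no bound at first treatment or at study exit.

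Consent may precede treatment or coincide with it. Under Protocol 13.1 an eligible subject is "provided the informed consent form to sign, or to return signed on Day 1 of TMS Treatment".

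On how events are compared, the Protocol synopsis (Safety Evaluation) looks at them "as occurring during the different treatment protocol administrations". SAP 6.6.1 says the comparison "between the experimental and the control group will be made descriptively". Neither document says how a single event is assigned to SoftStart (X) or standard Dash (Y).

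SAP 6.1.2 counts adverse-event onset among the dates that can set a subject's last contact, and so the duration in study.

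**The concern.** A mid-month default does little harm in a study lasting months. Here the whole treatment period is shorter than a month, so the 15th often lies outside it. Subjects who complete the crossover receive both treatments, so an event can be placed under X or Y only by knowing when it happened. If the imputed onset is used for that, the rule can place an event before any stimulation, after the subject has left, or under the other treatment.

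Better information is already collected. Adverse events are scheduled at every treatment visit (Protocol section 8; SAP Appendix A), and Protocol 17.4 covers those collected at stimulation visits. The session at which an event was first recorded should therefore be known even when its onset date is not.

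**Working it through.** **Inputs from the documents.** Ramp phase of r = 1 to 5 sessions, all on the randomized treatment A. Then four crossover sessions in the order B, A, B, A (Protocol 10.1 and 13.1). Total r + 4, that is 5 to 9 sessions. Participation up to about 14 days (Protocol synopsis). Consent before or on treatment day 1.

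**Assumptions not in the documents.** Monday-to-Friday sessions, start dates spread evenly over the calendar, each ramp length equally likely, equal event risk at each session. An imputed date on a weekend inside the treatment period is counted to the preceding session.

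**Step 1: the plan's own figure.** Five weekday sessions span 5 to 7 calendar days and nine span 11 to 13. This agrees with the stated 14 days.

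**Step 2: how often the 15th falls inside the treatment period.** Averaged over the five starting weekdays, the span is 6.6, 8.0, 9.4, 10.8 and 12.2 days for 5, 6, 7, 8 and 9 sessions. Weighting by number of sessions, because longer courses contribute more events:

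(5×6.6 + 6×8.0 + 7×9.4 + 8×10.8 + 9×12.2) / 35 = 343 / 35 = 9.8 days

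A mean month has 365.25 / 12 = 30.4 days, so the 15th falls inside treatment in 9.8 / 30.4 = 32% of cases and outside it in 68%.

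**Step 3: full enumeration.** 520 weekday start dates over two years × 35 combinations of ramp length and event session = 18,200 cases, each given the 15th of the event's month. Percentages are rounded.

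| Imputed onset | Consent before day 1 | Consent on day 1 |
|---|---|---|
| Before first session | 36% | 0% |
| After last session | 32% | 32% |
| In treatment, wrong treatment | 13% | 22% |
| In treatment, right treatment | 20% | 46% |

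In the first column the two in-treatment rows total 12.8% + 19.5% = 32.3% before rounding, which matches Step 2. With day-1 consent, a 15th that falls too early moves to day 1, hence to treatment A. The consent date cannot change the share after the last session.

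**Step 4: sensitivity for ramps of 1, 3 and 5 sessions.** The share on no treatment or the wrong one is 74% to 89% with earlier consent and 47% to 64% with day-1 consent. If weekend dates count as no treatment, these become 81% to 92% and 53% to 67%.

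**Step 5: fully unknown dates.** Ramp day 1 is always a session on treatment A. Of r + 4 sessions, r + 2 are on A, so the rule is wrong in 2 / (r + 4) of cases: 2/5 = 40% for r = 1 and 2/9 = 22% for r = 5. SAP section 4 says alternation continues for the next 4 treatments after the first switch. Read literally, that gives five crossover sessions, and the wrong share becomes 3 / (r + 5), or 50% to 30%.

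**Step 6: duration in study.** Take a subject with five sessions from Monday 1 to Friday 5 of a month and an event known only by month. The imputed onset is the 15th, 15 − 5 = 10 days after exit. Under 6.1.2 it would become the last contact date.

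**The case against.** The strongest reply is that the SAP never says X or Y is assigned from the onset date. The comparison in 6.6.1 is descriptive, the tabulations in 6.7 do not mention onset-based attribution, and the analyst could use the visit record. This stands in part: misattribution is a consequence only if the imputed date is used to assign treatment. But no other attribution rule is given, and 6.3 states that the 15th is used for analysis. The effect on duration in study does not depend on attribution.

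A second reply is that incomplete dates should be few. Protocol 17.4 asks for dates and times of occurrence, visits are nearly daily, and the SAP itself calls fully unknown dates rare. This stands, and it limits the impact.

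A third is that the result depends on when consent is signed. This also stands, so both cases are shown. With a long ramp and day-1 consent, slightly more than half of the imputed dates give the right treatment.

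A reader might go further and infer that both rules send most events to no treatment or the wrong one. The documents do not support that. Ramp day 1 is always a treatment day, and under equal risk per session the rule gives the right treatment in 60% to 78% of cases. Its weakness is that every such event is credited to the first-assigned treatment. Nor does treatment alternate daily throughout: the ramp sessions all use the randomized treatment.

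**Conclusion.** The point holds for the day-missing rule. Bounded only by consent, it puts the onset after the last session in about 32% of cases and on the right treatment in about 20% (consent before day 1) to 46% (consent on day 1). The rule for fully unknown dates is better, but it errs in one direction in 22% to 40% of cases. All these figures rest on the scheduling and risk assumptions listed with the calculation.

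This is a minor point. The documents give no expected number of incomplete dates, that number should be small, and the safety comparison carries no planned hypothesis test. The documents do not support a conclusion that the trial's safety comparison is materially distorted.

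**What to change.** Amend SAP 6.3 for adverse-event onset dates only and leave the date-of-death rule as it is:

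1. Attribute an event with an incomplete onset date to X or Y from the session at which it was first recorded.
2. Impute its onset to the date of that session.
3. Cap any imputed onset at study exit.
4. Keep events recorded before the first stimulation as pre-treatment; do not move them into the treatment period.

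One convention remains for the sponsor to settle in the same paragraph: how to attribute an event that is reported at a visit but said to have begun before that day's stimulation. In the crossover phase the preceding session used the other treatment.

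The cost is a few sentences in the SAP. No new data are needed, because adverse events are already recorded by visit.

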## **6.4 Subject Disposition**

The number of subjects in each analysis population will be presented along with reason for any exclusions. Subject accountability will be summarized by visit. The number of subjects who are enrolled, eligible for follow-up, and number completing clinical follow-up will be summarized for each protocol-required visit. In addition, the number of subjects who complete the study or exit early will be summarized by reason.

## **6.5 Demographics and Baseline Characteristics**

Descriptive statistics will be presented for all clinically relevant baseline demographic, medical history, and clinical characteristic variables, as well as other baseline characteristics.

## **6.6 Analysis of Study Endpoints**

### **6.6.1 Primary Safety Endpoint**

Comparison of the incidence, severity, and frequency of Adverse Events (AE) & Adjustments in Treatment Location between the experimental and the control group will be made descriptively.

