18.2 Analysis Plan

The primary outcome is the difference in comfort and pain observed between rTMS stimulation protocols using VAS comfort scores. The analysis will be performed on the sample of evaluable subjects, meaning those subjects with at least one post-treatment time point.

- Descriptive analysis of subject demographics and other baseline variables.

- Primary Outcome Assessment:

The Primary study outcome will be determined based on differences in the mean VAS ratings on a 0-10cm VAS scale for comfort between treatment arms.

- Secondary Outcome Assessment:

The Secondary objectives are to evaluate the ability to reach the prescribed treatment intensity, the time it takes to reach the prescribed treatment intensity, maximum treatment intensity reached, patient treatment preference and discontinuations due to treatment discomfort. Other treatment effects between the two treatment protocols will be explored.

- Comparison of the incidence, severity, and frequency of Adverse Events (AE) between the experimental and the control group will be made descriptively.
- Statistical methods employed to detect differences between the experimental and the control groups, for the above outcomes, may include a t-test, Chi-Square test, and Fisher's Exact test. For assessments including crossovers, a relevant method accounting for period effect, repeated measures, and randomized order will be utilized.
- Subgroup analysis will be performed based on initial comfort scores, group assignments or other variables.
- More detailed descriptions of the statistical methodology and analyses will be supplied in a separate SAP (statistical analysis plan).

ADMINISTRATIVE SECTION

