## 1 Introduction

This statistical analysis plan (SAP) describes the planned statistical methods to be used during the reporting and analysis of data and should be read in conjunction with the study protocol and case report forms (CRFs). Any revisions to the protocol or CRFs that impact the planned analyses may require updates to the SAP.

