### **6.2 Analysis Populations**

*The following analysis populations are defined for analysis:*

1. **Intent-to-treat (ITT):** *The ITT population is defined as all subjects randomized.*
2. **Modified Intent-to-Treat (mITT):** *The mITT population is defined as all subjects in the ITT population where treatment was initiated.*
3. **Per protocol (PP):** *The PP population is defined as all subjects in with no significant protocol deviation, or adverse event that could compromise the validity of their assessments.*
4. **Safety (SAF):** *The SAF population is defined as all subjects that were exposed to any study device or treatment.*

The primary analysis set for efficacy endpoints and results will be the mITT set, with any other analysis sets defined as optional and supportive. The primary analysis set for safety endpoints and results will be the SAF set, with any other analysis sets defined as optional and supportive.

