## **6.7 Safety Analyses**

Adverse events (AE) will be reported for the SAF population. AEs will be tabulated with the number of events and subjects with event for each event type and overall. Rates will be reported as the number of subjects who experience at least one event during the analysis interval out of the total number of subjects with follow-up to the beginning of the analysis interval. Serious adverse events will also be tabulated. The rate of all AEs and SAEs reported in the study will be reported.

All device deficiencies will be reported in listing format.

Statistical Analysis Plan		Page 13 of 18
Sponsor Neuronetics	Study Comfort Start	Version 1.0

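### Adverse events are compared between groups although every completer receives both protocols, and the SAP's counts and rates ignore how many sessions each protocol was given

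*SAP*

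**What the plan says.** The AE comparison is described in four places, and they do not match.

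- Protocol section 7, under Safety Evaluation, plans on "comparing the type, frequency, and severity of adverse events as occurring during the different treatment protocol administrations". This is a comparison by treatment received.
- Protocol 18.2 states: "Comparison of the incidence, severity, and frequency of Adverse Events (AE) between the experimental and the control group will be made descriptively". SAP 6.6.1 uses almost the same sentence for its primary safety endpoint, where the contrast is again "between the experimental and the control group will be made descriptively". Neither says whether a group is a randomised sequence or the sessions given under one protocol.
- SAP 6.7 states: "AEs will be tabulated with the number of events and subjects with event for each event type and overall". On rates it adds: "Rates will be reported as the number of subjects who experience at least one event during the analysis interval". The denominator is a count of subjects, not of sessions. The interval is not defined, and no split by X and Y is given.
- SAP 6.2 states: "The SAF population is defined as all subjects that were exposed to any study device or treatment". It has no rule for assigning an event to a protocol.

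On the design, protocol 10.1 and 13.1 give each subject 1 to 5 ramp sessions on the randomised protocol, then four alternating crossover sessions, two on each protocol.

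**The concern.** After the ramp there is no experimental or control group of subjects, because everyone who stays in the study has had both protocols. An analyst following SAP 6.6.1 and 6.7 must choose what a group is, and the tables then depend on that choice.

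Under treatment received, the two protocols need not be given for the same number of sessions. The imbalance comes from the ramp, which is spent entirely on the first-assigned protocol and ends when the target intensity is reached. A shorter time to target with SoftStart is the study's own hypothesis (protocol sections 7 and 9.1). If it is true, X is given in fewer sessions than Y. A raw count, or the share of subjects with at least one event, would then look better for X with no difference in risk per session. A reader of the primary safety table could take a difference in exposure for a difference in tolerability.

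**Working it through.** **Figures in the plan.** Neither document gives an AE rate or a session total for the AE comparison, and the sample size of 40 is stated not to rest on a power calculation (protocol 18.1, SAP 5). The one related figure, up to 9 study treatments (protocol 13.1), reproduces as 5 ramp + 4 crossover = 9.

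**Inputs from the documents.** 20 subjects start on each protocol; ramp length is 1 to 5 sessions; there are four crossover sessions, two on each protocol. (SAP 4 speaks of alternating for the next 4 treatments after the switch, which could be read as five sessions. Its following sentence and its Appendix A give four.)

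**Assumptions.** All sessions are completed, per-session risk is constant, sessions are independent, and no event carries over from one protocol to the other. The ramp lengths and the 5% risk below are illustrations and do not come from the documents.

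**1. By treatment received.** Let kX and kY be the ramp sessions in the X-first and Y-first arms.

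X sessions = 20(kX + 2) + 20 × 2; Y sessions = 20(kY + 2) + 20 × 2.

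| Ramp on X, Y | X sessions | Y sessions | Ratio Y/X |
|---|---|---|---|
| 3, 3 | 140 | 140 | 1.00 |
| 2, 3 | 120 | 140 | 1.17 |
| 1, 5 (limiting case) | 100 | 180 | 1.80 |

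Take ramps of 2 and 3 and a risk of 5% per session on both protocols.

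- Expected events: 0.05 × 120 = 6 on X and 0.05 × 140 = 7 on Y.
- Expected share of subjects with an event on X: the mean of 1 − 0.95^4 = 0.185 and 1 − 0.95^2 = 0.0975, which is 0.141, or 5.7 of 40.
- Expected share on Y: the mean of 1 − 0.95^5 = 0.226 and 0.0975, which is 0.162, or 6.5 of 40.

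The subject denominator in SAP 6.7 therefore narrows the gap slightly but does not remove it. Per session delivered, 6/120 = 7/140 = 5.0 events per 100 sessions, so the gap vanishes.

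**2. By randomised sequence.** With a ramp of k sessions in both arms, an X-first subject has k + 2 X sessions out of k + 4, and a Y-first subject has 2 out of k + 4. The share of the X–Y contrast that remains is (k + 2 − 2)/(k + 4) = k/(k + 4).

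- k = 1: 1/5 = 20%
- k = 2: 2/6 = 33%
- k = 5: 5/9 = 56%

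**3. Which reading the documents support.** The synopsis attributes events to the protocol being administered. SAP section 1 says that the SAP is to be read together with the protocol. SAP 6.6.2 introduces its VAS analyses with the same experimental and control wording, and two of the three then compare X averages with Y averages over all 40 subjects. All this points to treatment received, so step 1 is the main result and step 2 the consequence of the less likely reading.

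**The case against.** The strongest reply is that the intent is already clear. The synopsis gives the attribution, the SAP defers to the protocol, and the VAS analyses use X and Y by treatment received. This stands as a reason to prefer that reading. It does not supply a session denominator, which neither document gives, and it does not tell an analyst how to apply SAP 6.7.

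A reader might infer that a true AE difference will be diluted by 44% to 80%. Those figures are 1 − k/(k + 4) at k = 5 and k = 1, and they need the by-sequence reading, which the documents make less likely. A reader might also infer an excess of 80% in Y events. That needs every X-first subject to finish the ramp in one session and every Y-first subject to take five, and nothing in the documents supports it. With equal ramps there is no skew.

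Three further limits stand.

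- The comparison is descriptive, in an exploratory study without a power basis. No test, margin or stopping rule uses it.
- Protocol 17.1 excuses headache, dizziness and ear popping from AE recording unless they exceed what is normal for TMS, so counts may be small. Comfort scores, intensity reached and discontinuations for discomfort carry most of the tolerability evidence.
- Constant per-session risk is a simplification. Protocol 9.1 says that intensity and duration affect these events, and ramp sessions start at 90% MT. A pooled per-session rate would still mix intensities, which is why the phases should be shown apart.

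The undefined interval in SAP 6.7 could be taken as ramp and crossover separately, but the SAP does not say so.

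**Conclusion.** The point holds in a limited form. The SAP safety sections do not carry through the by-protocol comparison that the synopsis intends, and the rate in SAP 6.7 gives unequal results at equal per-session risk whenever ramp length differs between arms. The likely direction, if the study's hypothesis is right, is in favour of SoftStart. In the illustrative moderate case the effect is about one event (6 against 7), and it is zero with equal ramps. Only under the less likely by-sequence reading would the contrast shrink to between 20% and 56% of its size.

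These figures rest on constant per-session risk, completed sessions and 20 subjects per arm. The consequence is for how the AE tables are read; no error rate is affected. The change should be made because it is cheap and removes an artefact whose direction can be foreseen.

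**What to change.** In SAP 6.6.1 and 6.7, and for consistency in protocol 18.2:

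- Replace the group comparison with one by protocol. Attribute each AE to the protocol (X or Y) of the most recent session before onset, in line with the synopsis.
- For each protocol, report the sessions delivered, events per session delivered, and sessions with at least one event per session delivered. Alongside, give subjects with an event out of subjects exposed to that protocol.
- Show the ramp phase (between randomised arms) and the crossover phase (within subject, two sessions on each protocol) separately, without ranking one above the other. Define the analysis interval as these two phases.
- Keep the overall table for the safety population.

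The cost is SAP wording and one extra table. The data are already planned: AEs are assessed at every treatment visit (protocol section 8), their dates and times are recorded (protocol 17.4), and the protocol for each session follows from the randomised start and the alternation. The comparison stays descriptive, and small counts should be expected.
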